#### 4.1.4.3 Temporary treatment interruption and dose reduction

DLTs or those AEs requiring dose adjustment as indicated within the prescribing information, should be managed by treatment interruptions and subsequent dose reductions of the presumed causal study drug(s) according to the schedule described in [Table 4.1.4.3: 1](#). Please also refer to Section 4.2.3 for additional recommendations. In Part A, both Xentuzumab (BI 836845) and afatinib must be paused when a DLT occurs during the first treatment course. Dose reductions will apply to individual patients only and dose of Xentuzumab (BI 836845) and/or afatinib may be reduced independent of one another. Once the dose has been reduced, it cannot be increased later.

To prevent the development of more severe adverse events, treatment related AEs should be closely monitored and managed early and proactively as described in [Section 4.2.3](#).

Treatment should be paused until a patient has recovered from a drug-related AE to grade  $\leq 1$  or baseline. Baseline is defined as the CTCAE grade at the start of treatment. For patients who develop a DLT, treatment may be resumed at reduced dose according to the dose reduction scheme of the patient's starting dosage (Table 4.1.4.3: 1). If a patient has not recovered to Grade  $\leq 1$  or baseline within 14 days, study treatment must be permanently discontinued. In the event that the patient is deriving obvious clinical benefit according to the investigator's judgment, further treatment with study drug(s) will be decided in agreement between the sponsor and the investigator.

Diarrhoea and skin-related AEs are common side-effects of afatinib listed within the prescribing information. Please refer to the current afatinib prescribing information/SmPC for dose adjustment recommendations (except for the Course 1 of Part A if a DLT occurs, in which case both drugs need to be interrupted until AE recovery, refer to [Section 5.2.6](#)). When these AEs occur and are considered related to study treatment, the first dose modification is recommended to be made preferentially for afatinib.

In the event of any unrelated AEs or related non-DLT AEs, the investigator may choose to interrupt the medication (Xentuzumab (BI 836845) and/or afatinib) for up to 14 days, but no dose reduction should occur unless indicated in the current drug label/SmPC of afatinib. If the medication is interrupted for more than 14 days, the decision to continue with

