**Proprietary confidential information.**

**© 2016 Boehringer Ingelheim International GmbH or one or more of its affiliated companies. All rights reserved.**  
This document may not - in full or in part - be passed on, reproduced, published or otherwise used without prior written permission.

Table 4.1.4.3: 1 Dose reduction scheme by AE type and CTCAE Grade (Part A and Part B)

AE type and CTCAE Grade	Action	Dose reduction scheme
Events related to study drug:  - Diarrhoea Grade 2 persisting for 2 or more consecutive days (48 hours) despite adequate anti-diarrhoeal medication/hydration  - Nausea and/or Vomiting Grade 2 persisting for 7 or more consecutive days despite anti-emetic treatment/hydration  - Reduced renal function to $\geq$ Grade 2 as measured by serum creatinine, proteinuria or decrease in glomerular filtration rate of more than 50% from baseline  - Drug-related skin AE Grade $\geq 3$	
Pause afatinib treatment until patient has recovered to Grade <math>\leq 1</math> or baseline1. Xentuzumab (BI 836845) may be paused at the discretion of the investigator
 
Resume treatment at reduced dose according to schedule opposite.
 
If patient has not recovered to Grade <math>\leq 1</math> or baseline within 14 days study treatment must be permanently discontinued.
	
Afatinib
 
If patient was receiving 40 mg, resume treatment at a dose of 30 mg.
 
If patient was receiving 30 mg, resume treatment at a dose of 20 mg.
 
If patient was receiving 20 mg, discontinue afatinib.
 
Xentuzumab (BI 836845)
 
Reduce Xentuzumab (BI 836845) at investigator's discretion after interruption, but by no more than one level at a time. (1000mg (starting dose)->750mg (-1 dose level))
 
If patient need further dose reduction below 750 mg, discontinue BI836845.

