Grade 3	Symptomatic, interfering with ADL	
 
See grade 2
 
Topical steroids of higher potency (e.g. prednicarbate, mometasone furoate)
 
Consider oral antibiotics
 
See Section 4.1.4.3 for dose modification
 

Proprietary confidential information.

© 2016 Boehringer Ingelheim International GmbH or one or more of its affiliated companies. All rights reserved.

This document may not - in full or in part - be passed on, reproduced, published or otherwise used without prior written permission.

Table 4.2.3.2: 2 Grade specific treatment recommendations of skin reactions (con'd)

Severity (CTCAE grade)	Description 	Specific intervention
FISSURES		
Grade 1	Asymptomatic	

• Petroleum jelly, Vaseline® or Aquaphor for 30 minutes under plastic occlusion every night, followed by application of hydrocolloid dressing; antiseptic baths (e.g. potassium permanganate therapeutic baths, final concentration of 1:10,000, or povidone-iodine baths)

• Topical application of aqueous silver nitrate solutions to fissures

Grade 2	Symptomatic, not interfering with ADL	

• See grade 1

• Consider oral antibiotics.

• Afatinib and/or Xentuzumab (BI 836845) treatment interruption

Grade 3	Symptomatic, Interfering with ADL	

• See grade 2

1) May refer to CTCAE version 4.03 for updated description of grading

\* If grade 2 rash persists for  $\geq 7$  days despite treatment and is poorly tolerated by the patient, the investigator may choose to pause afatinib and/or Xentuzumab (BI 836845) treatment up to 14 days followed by a reduction in the dose of afatinib and/or Xentuzumab (BI 836845) according to the dose reduction scheme in [Table 4.1.4.3: 1](#).

If despite optimal supportive care and a treatment pause, grade 2 rash does not resolve to CTCAE Grade  $\leq 1$  within 14 days, treatment with afatinib and/or Xentuzumab (BI 836845) must be permanently discontinued. In the event that the patient is deriving obvious clinical benefit according to the investigator's judgement, further treatment with afatinib and/or Xentuzumab (BI 836845) will be decided in agreement between the sponsor and the investigator.

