\*\*CTCAE grade 3 (or greater) rash: may be treated in a manner similar to CTCAE grade 2 rash. In the event of CTCAE grade  $\geq 3$  rash, treatment with afatinib and/or Xentuzumab (BI 836845) should be paused until recovery to CTCAE grade  $\leq 1$ . Treatment should be resumed at a reduced dose (Table 4.1.4.3: 1). If CTCAE grade  $\geq 3$  rash does not resolve to CTCAE grade  $\leq 1$  within 14 days of stopping afatinib and/or Xentuzumab (BI 836845) treatment and despite optimal supportive care, the patient should not receive any further treatment with afatinib and/or Xentuzumab (BI 836845) and the End of Treatment visit should be performed.

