	B1	Informed consent not available / not done	
Inclusion criterion IN14 is not met.
 
or
 
Date of informed consent is missing.
	All

Proprietary confidential information © 2017 Boehringer Ingelheim International GmbH or one or more of its affiliated companies

Table 6.2:1 Important protocol violations (cont.)

Category/ Code	Description	Requirements	Excluded from	
	B2	Informed consent too late	Informed consent date was after Screening Visit date	None
	B3	Age limit for patient inclusion not adhered to	Patient's age < 18 as in IN1	All
C [2]		Trial medication and randomisation		
	C1	Time window violation for procedures performed at screening	Baseline disease assessment not within 30 days prior to first treatment. Create listing, decision at MQRM / RPM.	None
	C2	Trial medication not given according to protocol	Dose reduction scheme not followed (see CTP section 4.1.4.3); Administration of trial medication(s) not compliant. Indicated by medical review (i.e. where Administration of xentuzumab according to the protocol = 'No' and associated comments, or compliance data from afatinib with associated comments) Please note: This excludes the investigational treatment given outside the boundaries specified in the CTP (covered in Category C3).	None
	C3	Infusion time for the investigational treatment outside of CTP specific boundaries	Infusion duration of xentuzumab given < 50 minutes or > 200 minutes (Infusion time should be from 60 to 180 minutes, but the thresholds above are accepted). The exact duration of the infusion should be calculated taking interruptions into account. In case of missing administration times, the violation will not be considered important if administration according to protocol = 'Yes'.	None

Proprietary confidential information © 2017 Boehringer Ingelheim International GmbH or one or more of its affiliated companies

Table 6.2:1 Important protocol violations (cont.)

Category/ Code	Description	Requirements	Excluded from	
	C4	Patient assignment not followed	Patients do not receive the initial treatment they were allocated to.	None
D [2]		Concomitant medication		
	D1	Prohibited treatment during trial conduct phase	Exclusion criterion EX17 met or Indicated by medical review of concomitant therapy use during study treatment.	None
E [2]		Missing Data		
	E1	Imaging assessments not done according to CTP instructions	Imaging assessment should be performed at screening and several time points thereafter (see TSAP Section 6.7.2).	None

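### Protocol 4.2.3.2 permits a xentuzumab reduction for persistent, poorly tolerated Grade 2 rash that 4.1.4.3 does not allow, and the two sections also differ on skin events of Grade 3 or higher

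*Protocol*

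**What the plan says.** **Grade 2 rash, protocol 4.2.3.2.** The note to Table 4.2.3.2: 2 applies when the rash has lasted at least 7 "days despite treatment and is poorly tolerated by the patient". In that case "the investigator may choose to pause afatinib and/or Xentuzumab (BI 836845) treatment up to 14 days followed by a reduction in the dose". The reduction can be of either drug or both, following the scheme in Table 4.1.4.3: 1.

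**Related non-DLT events, text of 4.1.4.3.** "In the event of any unrelated AEs or related non-DLT AEs, the investigator may choose to interrupt the medication" for up to 14 days, "but no dose reduction should occur unless indicated in the current drug label/SmPC of afatinib". The same section refers diarrhoea and skin events to the afatinib label for dose adjustment, prefers afatinib for the first modification, points to Section 4.2.3 for further recommendations, and says that a reduced dose cannot be raised again.

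**Table 4.1.4.3: 1.** The skin trigger is a drug-related skin event of Grade 3 or higher. Afatinib must be paused and resumed at a lower dose. For the other drug, "Xentuzumab (BI 836845) may be paused at the discretion of the investigator", with reduction also at discretion. The footnote on unrelated events rules out dose reduction for those events only.

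**Grade 3 or higher rash, 4.2.3.2.** The note says "treatment with afatinib and/or Xentuzumab (BI 836845) should be paused until recovery to CTCAE grade" 1 or lower, then resumed at a reduced dose under Table 4.1.4.3: 1.

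**Fissures, Table 4.2.3.2: 2.** The Grade 2 row lists "Afatinib and/or Xentuzumab (BI 836845) treatment interruption". The Grade 3 row only refers back to Grade 2. The Grade 3 rows for acneiform rash, pruritus and xerosis each refer to 4.1.4.3 for dose modification.

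**SAP Table 6.2:1, code C2.** One requirement reads "Dose reduction scheme not followed (see CTP section 4.1.4.3").

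**The concern.** The protocol names skin events among the most common effects of afatinib, so these instructions are likely to be used. Two investigators with the same patient, each relying on a different section, could reach different permanent doses. Reductions enter several descriptive outputs directly: the number of patients with a reduction, time to first reduction, total dose and dose intensity (SAP 5.4.2), and adverse events leading to dose reduction, listed by drug (SAP 7.8.1). They also alter the xentuzumab exposure behind the Part B response rate, though that effect is indirect and the documents give no means of sizing it. The dose-reduction item in C2 cites only CTP 4.1.4.3, so a reviewer applying it could query a reduction that 4.2.3.2 allowed.

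**Working it through.** This is mainly a comparison of text. The plan gives no figure of its own to reproduce.

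**1. Is Grade 2 rash a non-DLT event?** The named rash criterion in 5.2.6 starts at Grade 3, so Grade 2 rash is non-DLT by default. In Part A the last criterion lets an event needing reduction under the afatinib label be confirmed as a DLT. DLTs are investigated only in Part A (5.2.7), so that route is closed in Part B.

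**2. Grade 2 rash that meets the note's conditions, case by case.**

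| Action | Note in 4.2.3.2 | Text of 4.1.4.3 | Result |
|---|---|---|---|
| No reduction | Allowed, since the note is optional | Allowed | No conflict |
| Afatinib reduced, label indicates it | Allowed | Allowed by the exception | No conflict |
| Afatinib reduced, label does not indicate it | Allowed | Not allowed | Conflict |
| Xentuzumab reduced | Allowed | Not allowed; the only exception is the afatinib label | Conflict |

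The label is not in the documents, so the second and third rows both stay open.

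**3. Is 4.1.4.3 consistent with itself?** Its text applies the no-reduction statement to unrelated and to related non-DLT events, with the label exception. The table footnote applies it to unrelated events only, with no exception. A related Grade 2 rash falls under the first and outside the second.

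**4. Grade 3 or higher rash.** Pausing xentuzumab alone would satisfy the literal wording of the 4.2.3.2 note but not the table's skin row, which requires an afatinib pause. In Part A, a rash that is a DLT in course 1 requires both drugs to be paused. In Part B the skin row governs and the difference in wording remains.

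**5. Grade 3 fissures.** The skin table leads to interruption of either drug or both. Table 4.1.4.3: 1 requires an afatinib pause and reduction for any drug-related skin event of that grade.

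**6. Size of one xentuzumab reduction.** The step is 1000 to 750 mg: (1000 − 750)/1000 = 25%. There is one step only, since 750 mg is the lowest level allowed. SAP 5.4.2 sets the planned dose as the planned dose per infusion times the number of visits with an infusion. For *n* infusions, *m* of them at 750 mg:

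intensity = 100 × [1000(*n* − *m*) + 750*m*]/(1000*n*) = 100 − 25*m*/*n*.

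If half the infusions are reduced, intensity is 100 − 12.5 = 87.5%.

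**7. How many patients might meet the note?** The documents give no rate. Assuming 10%, 20% or 30% of the 18 Part B patients:

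- expected number, 18*p*: 1.8, 3.6, 5.4;
- chance of at least one, 1 − (1 − *p*)^18: 0.85, 0.98, 0.998.

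These count patients who would meet the note's conditions. They do not count xentuzumab reductions, which also need an investigator to choose a reduction and to choose it for that drug.

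**The case against.** The strongest answer is that the two sections can be read together. Section 4.1.4.3 itself sends the reader to 4.2.3, so the rash note could be the specific rule within a general one. The note's reference to Table 4.1.4.3: 1 could mean only the dose steps, with the note supplying the trigger. The opening of 4.1.4.3 speaks of reducing the presumed causal drug or drugs, and an alternative scheme may be agreed with the sponsor's clinical monitor. This softens the xentuzumab conflict but does not remove it. That opening sentence covers DLTs and events for which prescribing information calls for adjustment, and the documents cite none for xentuzumab, whose listedness reference is the Investigator's Brochure (8.4.1). An agreed exception is not a stated rule.

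For Grade 3 or higher rash, the stated preference for modifying afatinib first makes a xentuzumab-only pause unlikely in practice. For Grade 3 fissures, the skin table is silent on reduction and does not forbid it, and the general skin row can still apply. Both points are fair; what remains is a difference in wording.

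A reader might infer that following either section breaches the other and that the patient is then automatically recorded as an important protocol violation. The documents do not support that. The Grade 2 note is permissive, so making no reduction breaches nothing. Category C violations are identified by individual review, from a working list of potentially important violations. C2 excludes nobody, and there is no per-protocol set (SAP 6.2).

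**Conclusion.** The point holds in a limited form. For persistent, poorly tolerated Grade 2 rash, 4.2.3.2 permits a xentuzumab reduction that the text of 4.1.4.3 does not allow. Conflict over afatinib cannot be shown without the label. The text and table footnote of 4.1.4.3 differ in scope, and the two sections do not match on the drug paused for Grade 3 or higher rash or on Grade 3 fissures.

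The consequence per affected patient is a permanent 25% xentuzumab step, possibly queried under C2. The number affected is unknown; the range for patients meeting the note rests wholly on the assumed 10–30% rate. The analyses are descriptive, so no test or error rate is affected. What is at stake is consistent dosing across sites and clear reporting of exposure and dose reductions.

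**What to change.** The sponsor decides the rule and states it in the same terms in 4.2.3.2, the text of 4.1.4.3, Table 4.1.4.3: 1 and its footnote. Four items need settling:

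1. whether a Grade 2 rash can lead to dose reduction, under what conditions, and of which drug;
2. which events the no-reduction statement covers, so that text and footnote agree;
3. which drug or drugs are paused for Grade 3 or higher rash;
4. how Grade 3 fissures are handled, with a reference to 4.1.4.3 if the general skin row is meant to apply.

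SAP code C2 should then cite the reconciled rule. Reductions already made under 4.2.3.2 should be identified as such at the review meeting, so that their status is decided openly.

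The cost is wording in two protocol sections and one SAP table entry. No new data are needed, and the SAP says the violation list may stay open until the final planning or database-lock meeting.

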 In the event that the patient is deriving obvious clinical benefit according to the investigator's judgement, further treatment with afatinib and/or Xentuzumab (BI 836845) will be decided in agreement between the BI clinical monitor and the investigator.

In the event of any unrelated adverse events, the investigator may choose to interrupt the medication (afatinib and/or Xentuzumab (BI 836845)) for up to 14 days, but no dose reduction should occur. If the medication is interrupted for more than 14 days, the decision to continue with afatinib and/or Xentuzumab (BI 836845) will be made by the BI clinical monitor in agreement with the investigator.

 except alopecia, infusion reaction and allergic reaction

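### For a drug-related Grade 3 or higher rash unresolved at 14 days in a patient with obvious clinical benefit, Protocol Section 4.2.3.2 bars further treatment while Section 4.1.4.3 lets it be agreed.

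*Protocol*

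**What the plan says.** Three places in the Protocol bear on a severe rash that persists through a treatment pause.

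- **Section 4.2.3.2, note on Grade 3 or higher rash.** Treatment is paused until recovery to Grade 1 or less and resumed at a reduced dose taken from Table 4.1.4.3: 1. If the rash has not resolved within 14 days, "despite optimal supportive care, the patient should not receive any further treatment with afatinib and/or Xentuzumab (BI 836845) and the End of Treatment visit should" take place. No exception follows.
- **Section 4.1.4.3, Table 4.1.4.3: 1, first row.** The row lists "Drug-related skin AE Grade" 3 or higher among its events. Afatinib is paused, and "Xentuzumab (BI 836845) may be paused at the discretion of the investigator". Without recovery to Grade 1 or less "or baseline within 14 days study treatment must be permanently discontinued", and that sentence carries footnote 2: "In the event that the patient is deriving obvious clinical benefit according to the investigator's judgement, further treatment with afatinib" and/or xentuzumab is decided jointly by the sponsor's clinical monitor and the investigator. The body text of Section 4.1.4.3 gives the same default and the same exception, naming the sponsor instead of the clinical monitor.
- **Section 4.2.3.2, note on Grade 2 rash, directly above the Grade 3 note.** If the rash does not resolve within 14 days, "treatment with afatinib and/or Xentuzumab (BI 836845) must be permanently discontinued. In the event that the patient is deriving obvious clinical benefit", further treatment is decided between sponsor and investigator.

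The SAP's list of important protocol violations (Table 6.2:1) has code C2 for trial medication not given according to protocol. It cites Protocol Section 4.1.4.3 for the dose reduction scheme and does not cite Section 4.2.3.2.

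**The concern.** The Grade 3 note and the table's first row describe the same patient at the same time. One ends treatment outright. The other ends it unless an agreement to continue is reached. The note sends the reader to the table for the reduced dose, so a site handling this event will have both rules in front of it.

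At stake is a stop-or-continue decision, after a severe and persistent toxicity, in a patient who appears to be benefiting. The two places also differ on whether there is a decision to make. A site that follows the note has no reason to contact the clinical monitor; a site that follows the table does. Treatment duration and discontinuation summaries would then depend in part on which page was used.

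**Working it through.** No formula governs this point, and the plan gives no figure to reproduce. The check is a comparison of the two rules, followed by a rough look at size.

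**Step 1. The rules side by side, for a drug-related Grade 3 or higher rash unresolved at 14 days**

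| Patient | Section 4.2.3.2, Grade 3 note | Section 4.1.4.3, body text and Table 4.1.4.3: 1 with footnote 2 | Conflict? |
|---|---|---|---|
| No obvious clinical benefit | No further treatment | Permanent discontinuation | No |
| Obvious clinical benefit | No further treatment | Further treatment open to agreement | Yes |

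The 14-day limit is the same in both places. The conflict lies in the second row only.

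**Step 2. Can the missing exception be read in?** The parallel 14-day notes in Section 4.2.3 write it out: the Grade 2 rash note, and the starred note to the diarrhoea table for Grades 3 and 4. The Grade 3 rash note does not. It opens by allowing management much like that of a Grade 2 rash, which might bring the Grade 2 exception with it, yet it closes with an explicit bar. The text supports both a deliberate omission and a drafting slip.

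**Step 3. Does any passage set an order of precedence?** Section 4.1.4.3 points to Section 4.2.3 for additional recommendations. The Grade 3 acneiform rash row in Section 4.2.3.2 points to Section 4.1.4.3 for dose modification, and the Grade 3 note points to Table 4.1.4.3: 1. The references run both ways, and none says which text governs when they disagree.

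**Step 4. The End of Treatment visit.** The Grade 3 note speaks of afatinib and/or xentuzumab and then requires this visit. Section 3.1 ties the visit to permanent discontinuation of both drugs, while Section 4.1.4.3 allows one drug to be discontinued alone. Whether the visit is due after a single-drug stop under the note is not stated.

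**Step 5. Size.** Section 4.2.3 places dermatologic events and diarrhoea as the commonest afatinib side effects but gives no rate for Grade 3 or higher rash, for non-resolution at 14 days, or for obvious benefit among such patients. The following is an illustration on assumed rates only:

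- Unresolved severe rashes, assuming 5% to 15% of 42 patients have one and a quarter are unresolved: 42 × 0.05 × 0.25 = 0.5 to 42 × 0.15 × 0.25 = 1.6. This is not a count of conflicts, because it includes patients without obvious benefit.
- Conflicts, if the share with obvious benefit equalled the 15% to 25% response rates tabulated in Section 7.6: 0.525 × 0.15 = 0.08 to 1.575 × 0.25 = 0.4.

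If stable disease also counted as benefit, the second range would rise, but it could not pass the first.

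**The case against.** The strongest case on the other side is that Section 4.1.4.3 is plainly the operative scheme. Section 4.2.3.2 is headed as recommendations, Section 4.2.1 describes the Section 4.2.3 content as suggested treatments, and the note says should where the table says must. Section 4.1.4.3 states the exception twice. Item 7 of the discontinuation criteria in Section 3.3.4.1 also allows continuation by agreement after both drugs have been interrupted for more than 14 days. All of this makes Section 4.1.4.3 the likelier reading. It does not settle the matter: the note is an explicit instruction not to treat, and no text says that it gives way.

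Four stronger readings might be inferred and are not supported.

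- **That the stopping rule is undetermined for every unresolved severe rash.** Both places stop treatment by default; only patients with obvious clinical benefit are in dispute.
- **That sites could go their own way, each fully compliant.** Continuation always needs agreement from the sponsor or its clinical monitor, so no site can continue alone. A site that continues under the table also departs from the note.
- **That the two places conflict on which drug is paused.** The table's first row pauses afatinib, with xentuzumab at discretion, which largely fits within the note's and/or. The second row, covering dose-limiting toxicities and other severe drug-related events, uses and/or as well.
- **That the analysis is compromised.** C2 already cites Section 4.1.4.3 alone, is decided by individual review, and excludes no patient from any analysis.

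**Conclusion.** The contradiction is real and stands in the current text. It is limited to a drug-related Grade 3 or higher rash not recovered within 14 days in a patient judged to have obvious clinical benefit. For that patient one section forbids further treatment and the other allows it by agreement.

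The number of patients affected cannot be computed from the documents and is probably very small. Analysis sets, the primary endpoint definition and the sample size are not directly affected. An indirect effect on efficacy is possible: if stopping leads to another anti-cancer therapy, the window for best overall response closes (SAP Section 5.1.2) and duration of response is censored (SAP Table 5.2.2.2: 1).

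The conclusion rests on reading a drug-related Grade 3 or higher rash as falling within the table's skin-event row, and on there being no precedence statement in the text available. The point deserves correction because it concerns stopping for a severe toxicity and is cheap to resolve.

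**What to change.** Reconcile the body text of Section 4.1.4.3, the first row of Table 4.1.4.3: 1 with footnote 2, and the Grade 3 note in Section 4.2.3.2, so that one rule governs this case. State it once in Section 4.1.4.3, name there who must agree if agreement is part of the rule, and replace the stopping sentence in the Grade 3 note with a reference to it. Say whether the End of Treatment visit applies when only one drug is stopped. Which rule applies is for the sponsor's medical team to decide.

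SAP code C2 needs no rewording, because it already cites Section 4.1.4.3.

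The cost is a short protocol clarification and notice to sites. It needs no new data, but under Protocol Section 8.1 it goes through the usual ethics committee and authority approval for amendments.
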